6.1.2 Treatment duration

The duration of treatment with eltrombopag will be based on the reasons described below and other reasons for early withdrawal ([Section 7.2.3.17.2.3.1](#)):

- If no partial or complete hematological response is observed at 16 weeks and maintained afterwards, the patient will be withdrawn from the study.
- In patients achieving complete response without transfusion support for a minimum of 8 weeks, the dose of eltrombopag may be reduced by 50%, and discontinued if counts remain stable after 8 weeks at the reduced dose. If relapse occurs after eltrombopag discontinuation, eltrombopag can be reintroduced at the last effective dosage.
- If new clonal cytogenetic abnormalities associated with dysplastic bone marrow findings are observed such as monosomy 7, eltrombopag should be permanently discontinued.

- If the patient develops myelodysplastic syndrome (MDS) or acute myeloid leukemia (AML) assessed by sensitive methods, eltrombopag will be permanently discontinued.
- If other non-clonal and/or cytogenetic abnormalities with uncertain meaning not previously observed and not associated with worsening blood counts or bone marrow dysplastic, the decision of discontinuing eltrombopag is up to the investigator, based on a more frequent bone marrow aspirate monitoring of cytogenetic abnormalities and dysplastic findings.
- If relapse of previous hematological disease occurs, eltrombopag will be permanently discontinued.
- If patient receives a new HSCT, eltrombopag will be permanently discontinued

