7.2.3 Final visit (or Early withdrawal)

For patients who complete the 36-weeks of study treatment administration and/or assessments, or permanently stop taking study treatment for any reason, this visit should be performed 30 days after the last dose of eltrombopag:

- Supportive care (see [Section 6.3.1.1 / 7.3.1.2](#))
- Physical examination (See [Section 7.3.2.1](#)).
- Karnofsky performance status (See [Section 7.3.2.2](#))
- Weight (See [Section 7.3.2.3](#))
- Vital signs (See [Section 7.3.2.4](#))
- Hematology biochemistry and other analysis (See [Section 7.3.2.5](#))
- Urine or serum pregnancy test should be performed in women of childbearing potential (See [Section 7.3.2.6](#)).
- Blood smear (See [Section 7.3.2.5](#))
- ECG (See [Section 7.3.2.7](#))
- Ophthalmological monitoring (see [Section 7.3.2.8](#))
- Record any concomitant medication (See [Section 6.3](#))
- Record adverse events (See [Section 8.1](#)). If required (per investigator's opinion), another visit could be scheduled to follow up properly the patient's AE/SAE. This will be considered as an unscheduled visit, and the assessments to be made will be at the discretion of the investigator. Results will become part of the patient's medical history.

Patients lost to follow-up should be recorded as such on the CRF. For patients who are lost to follow-up, the investigator should show "due diligence" by documenting in the source documents steps taken to contact the patient, e.g., dates of telephone calls, registered letters, etc. At a minimum, all patients who discontinue treatment, including those who refuse to return for a final visit, will be contacted by phone for safety assessment during the 30 days following the last dose of study treatment.

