7.2.4 Follow-up for survival

All patients who discontinue from the study, regardless the reason of discontinuation, will be followed for survival for 24 and 36 weeks, unless they withdraw their consent, die or are lost-to follow-up, in which case will be censored at the last contact/follow-up.

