10.4.3 Handling of missing values/censoring/discontinuations

The reason for discontinuation from study will be summarized and listed, along with dates of first and last study drug, duration of exposure to study drug and date of discontinuation for each patient.

Other missing data will be noted as missing on appropriate tables/listings.

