10.5.1 Other efficacy objective(s)

- To determine the response in each haematological lineage separately, the absolute frequency and valid percentage of patients who have a response in the neutrophil, platelet, and Hb lineages separately after 16, 24 and 36 weeks of eltrombopag, will be presented with the 95% CI. Descriptive statistics will also be provided between baseline and weeks 16, 24 and 36 for ANC, platelets and hemoglobin levels, and the appropriate paired exploratory tests will be done according to the type of distribution (parametric or not) to assess the statistical significance of the changes.
- To evaluate the overall hematological response rate (partial and complete) at 24 and 36 weeks after the initiation of eltrombopag, the frequency and percentage distribution and the corresponding 95% CI will be provided. This CI will be constructed as for the primary efficacy endpoint. Descriptive statistics will also be provided between baseline and week 24 and week 36 for ANC, platelets count and hemoglobin levels, and the appropriate paired exploratory tests will be done according to the type of distribution (parametric or not) to assess the statistical significance of the changes.
- To evaluate transfusion independence, the percentage of patients who were previously transfusion-dependent and do no longer require a RBC or platelet transfusion before and after the first 16 weeks of treatment will be calculated along with the 95% CI. This CI will be constructed as for the primary efficacy endpoint. The period where patients did not receive any platelet or RBC transfusions during the treatment period and follow-up will also be analyzed.

- To evaluate the discontinuation or reduction of concomitant G-CSF and/or EPO therapy, the percentage of patients who discontinue or reduce by $\geq 50\%$ from baseline the use of concomitant G-CSF and/or EPO therapy will be calculated along with the 95% CI. This CI will be constructed as for the primary efficacy endpoint.
- Overall survival, defined as the duration from inclusion in the study to date of death (whatever the cause), will be estimated with the Kaplan-Meier curves method and two-sided 95% CI for the estimated median. All patients who discontinue from the study, regardless the reason of discontinuation, will be followed for survival for 24 and 36 weeks, unless they withdraw their consent, die or are lost-to follow-up, in which case will be censored at the last contact.

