### **3 STATISTICAL METHODS**

Quantitative variables are described with measures of central tendency and dispersion: mean, median, SD, Q1, Q3, minimum and maximum).

Qualitative variables are described using absolute and relative frequencies (N, %). Two percentage columns are presented, total percentage (total %) and valid percentage (valid %), that is, the percentage over the sum of valid responses plus missing values and the percentage over the total of valid responses. When there are not missing values both of them are equal, and then only one will be show.

[figure not shown]
In the analysis of contingency tables as well as for the comparison of proportions and / or frequency distributions, the chi-square test (or Fisher's exact when appropriate) will be used.

For dependent samples, parametric (t-test paired) or non-parametric (Wilcoxon) statistical tests will be performed depending on the distribution of the sample.

The "time to event" variables (overall survival) will be analyzed using the Kaplan-Meier method.

These tests will be used in all bilateral cases and with a level of significance of 0.05. In cases where a p-value less than 0.05 appears, it refers to the existence of statistical significance.

Data will be analyzed using SPSS v22.0.

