### 10.1 Primary objective

**To evaluate the efficacy of eltrombopag for poor graft function on overall hematologic response (partial and complete) as determined by platelets, hemoglobin and neutrophil counts, by 16 weeks after the initiation of eltrombopag.**

It will be calculated:

- The overall response rate, defined as the percentage of patients who have a hematological response (partial and complete) by 16 weeks after the initiation of eltrombopag. If the patient hasn't response in that week because was exit from the study before week 16 and in the last evaluation had a partial or complete response, also be considered as responder.

### 10.2 Secondary objective 1

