- To assess if there are statistical significance differences in ANC between baseline and week 36, it will be applied the appropriate paired test (T-test paired or Wilcoxon, depending the distribution of sample).
- To assess if there are statistical significance differences in platelets between baseline and week 24, it will be applied the appropriate paired test (T-test paired or Wilcoxon, depending the distribution of sample).
- To assess if there are statistical significance differences in platelets between baseline and week 36, it will be applied the appropriate paired test (T-test paired or Wilcoxon, depending the distribution of sample).
- To assess if there are statistical significance differences in hemoglobin between baseline and week 24, it will be applied the appropriate paired test (T-test paired or Wilcoxon, depending the distribution of sample).
- To assess if there are statistical significance differences in hemoglobin between baseline and week 36, it will be applied the appropriate paired test (T-test paired or Wilcoxon, depending the distribution of sample).

### 10.3 Secondary objective 2

**To evaluate the long-term efficacy of eltrombopag on overall hematologic response (partial and complete) at 24 and 36 weeks after the initiation of eltrombopag.**

It will be calculated:

- Percentage of patients who have secondary overall hematological response at 24 weeks, defined as the maintenance of a partial or complete response at 24 weeks.
- Percentage of patients who have secondary overall hematological response at 36 weeks, defined as the maintenance of a partial or complete response at 36 weeks.

[figure not shown]
### 10.4 Secondary objective 3

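### Lineage response at weeks 24 and 36 is reported as a valid percentage, which leaves out most patients withdrawn for non-response

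*SAP*

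**What the plan says.** **Who has counts.** Protocol 6.1.2: "If no partial or complete hematological response is observed at 16 weeks and maintained afterwards, the patient will be withdrawn from the study". For the final visit, protocol 7.2.3 says "this visit should be performed 30 days after the last dose of eltrombopag". Under protocol 7.2.4, patients who have left the study "will be followed for survival for 24 and 36 weeks"; no further blood counts are scheduled.

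**Which percentage.** For lineage response after 16, 24 and 36 weeks, protocol 10.5.1 names "the absolute frequency and valid percentage of patients who have a response in the neutrophil, platelet, and Hb lineages separately", with a 95% CI. SAP section 3 presents two columns when values are missing: "the percentage over the sum of valid responses plus missing values and the percentage over the total of valid responses". The first is the total %, the second the valid %. SAP 10.2 lists the lineage items simply as percentages of patients.

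**How absent values are scored.** SAP 10.1 has one early-exit rule. It concerns a patient who "was exit from the study before week 16 and in the last evaluation had a partial or complete response, also be considered as responder". It stops at week 16 and can only add responders. Protocol 10.4.3 summarizes and lists reasons and dates of discontinuation, then adds: "Other missing data will be noted as missing on appropriate tables/listings". Neither SAP 10.2 nor SAP 10.3 says how a patient withdrawn for non-response is scored at week 24 or 36.

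**Overall response.** SAP 10.3 has the week-36 endpoint "defined as the maintenance of a partial or complete response at 36 weeks", and a matching one for week 24. Protocol 10.5.1 asks for a percentage here, without the word valid, and builds its CI as for the primary endpoint.

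**The concern.** The counts are absent because treatment failed, and the design makes them absent. A valid percentage takes those failures out of the denominator and leaves the numerator alone. What remains is close to a rate among patients retained because they responded in at least one lineage. It can look high when few treated patients respond in that lineage, and the CI attached to it is shifted in the same way. In a single-arm study there is no control group to reveal the selection, so a reader may take the figure as the long-term response rate of treated patients.

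**Working it through.** **1. The plan's own figure.** Protocol 10.7: n = 33, assumed response 45%, one-sided 95% Clopper-Pearson lower limit 30.1%. The F formula in protocol 10.4.2 equals the 5% quantile of a Beta(x, n − x + 1) distribution. With x = 0.45 × 33 = 14.85 it gives 30.08%, which reproduces the plan. The nearest whole count, 15/33 = 45.5%, gives 30.5%.

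**2. Patients who leave at week 16.** 33 − 15 = 18 at the design rate.

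**3. Do they have later counts?** Days come from protocol Table 7-1, with ±3 days for these visits.

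- Stop at week 16: 113 + 30 = day 143, inside the week-20 window (138–144). No week-24 or week-36 count.
- Stop at week 20: 141 + 30 = day 171, inside the week-24 window (166–172). This patient could supply a week-24 value if visits are assigned by date.
- Stop at week 30: 211 + 30 = day 241, outside the week-36 window (250–256).

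So withdrawn patients mostly, though not always, lack the value.

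**4. Size of the distortion.** For platelets every patient has the baseline deficit (mandatory in protocol 5.1), so both percentages share a numerator and their ratio is 33 divided by the number with counts. If all 15 week-16 responders still have counts, that is 33/15 = 2.2. With 20 or 10 such responders it is 33/20 = 1.65 or 33/10 = 3.3.

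**5. Illustration at week 36.** The losses are assumed; the documents give no maintenance rate. Of 15 week-16 responders, 2 lose response at week 20 and 1 each at weeks 24, 30 and 36. Withdrawal is strict, so 15 − 2 − 1 − 1 = 11 have week-36 counts. Lineage counts are also assumed. Protocol 10.5.1 does not state the form of the lineage CI; the primary endpoint's one-sided limit is used here.

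| Week 36 | Withdrawn counted as non-responders | Valid % |
|---|---|---|
| Platelets | 9/33 = 27.3% (lower limit 15.0%) | 9/11 = 81.8% (53.0%) |
| Neutrophils, 16 with baseline deficit | 4/16 = 25.0% (9.0%) | 4/5 = 80.0% (34.3%) |

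The 16 is a rough guide. In the six-patient series in protocol 1.2.1.2, 2 responders are given as 66.6%, so 3 of 6 were neutropenic, and half of 33 is about 16. Entry criteria differ.

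**6. The neutrophil denominator.** A neutrophil response requires pretreatment ANC <1,000/µL. A plain FAS denominator would give 4/33 = 12.1% (4.2%), which is too low because it includes patients who cannot meet the definition. The same applies to hemoglobin.

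**7. Sensitivity to the assumed loss, for overall response.** Let h be the loss per visit at weeks 20, 24, 30 and 36. At week 36 the FAS rate is 15(1 − h)⁴/33 and the valid rate is 1 − h.

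- h = 5%: FAS 37.0%, valid 95%.
- h = 20%: FAS 18.6%, valid 80%.

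The direction does not depend on h; the size does.

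**The case against.** The strongest reply is that the full-sample figure is already planned. SAP section 3 prints the total % beside the valid %, and SAP 10.2 does not repeat the word valid. If withdrawn patients are kept as missing rows, the total % for platelets equals non-responder scoring, so 9/33 would stand next to 9/11. Attrition is visible too: SAP section 8 counts patients stopped at 16 weeks for no response and those on treatment in week 36, and SAP section 7 tabulates unsatisfactory therapeutic effect as a reason for leaving. This stands, and it limits the harm. It does not remove the point. Protocol 10.5.1 names the valid percentage and puts the CI with it, and for neutrophils and hemoglobin a total % over all 33 errs the other way.

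Withdrawal may also be softer than assumed. Protocol 7.2.3.1 says patients may be withdrawn, and patients who stop because of efficacy stay on visits. Any patient kept on with counts narrows the gap.

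A reader might infer that overall response at weeks 24 and 36 has the same defect. The documents do not support that. SAP section 4 assigns these analyses to the FAS, the CI follows the primary formula in which n is the sample size, and a patient withdrawn for non-response cannot be maintaining a response. Only an explicit sentence is lacking.

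**Conclusion.** The point holds for lineage response at weeks 24 and 36. The percentage named in protocol 10.5.1, read with SAP section 3, drops documented failures and inflates both the rate and its CI. At the design rate about 18 of 33 patients leave the denominator at week 16, so the platelet figure is at least 33/15 = 2.2 times the FAS figure if only week-16 responders have later counts, and 3 times in the illustration (33/11). This rests on strict withdrawal and on final-visit counts not standing in for the scheduled week; the illustrated rates also rest on assumed losses and lineage counts.

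For overall response a clarification is enough. A reader might also infer that the trial's main conclusion is at risk. It is not: withdrawal for non-response follows the week-16 assessment, and neither the primary result nor the sample size changes. Nor does the argument justify scoring every patient without a count as a failure. A continuing responder who misses a visit is not a documented failure. The affected endpoints are secondary and descriptive, but they bear on how durable the effect is, and the change is worth making before analysis.

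**What to change.** **Lineage response (protocol 10.5.1 and SAP 10.2).** At weeks 24 and 36, replace the valid percentage with one that counts patients who died, or were withdrawn for non-response or loss of response, as non-responders. Attach the 95% CI to it. Denominators: the FAS for platelets; FAS patients with pretreatment ANC <1,000/µL for neutrophils; FAS patients with pretreatment Hb <100 g/L for hemoglobin.

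**Overall response (SAP 10.3).** Add a sentence confirming that these patients count as not maintained and that the CI goes with the FAS figure. Give the share of week-16 responders as a labelled second line; in the illustration that is 10/15 = 66.7% (lower limit 42.3%) beside 10/33 = 30.3% (17.5%).

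**Other absent values.** List separately any patient still on study who missed the visit, and any responder who left for an unrelated reason. Handle them in a pre-stated sensitivity line and do not score them automatically as failures.

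**Cost.** A few sentences and no new data; reasons for leaving are already collected (SAP section 7). The protocol wording needs a written amendment under protocol 12.1, or a documented change in the SAP. The reported rates will be lower.

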**To evaluate the transfusion independence for red blood cells (RBC) and/or platelets after the initiation of eltrombopag.**

It will be calculated:

- The patient receive at least one transfusion before start treatment (No / Yes) (data in section “Supportive Care Record”).
- The patient receive at least one transfusion after start treatment and before week 16 (No / Yes) (data in section “Supportive Care Record”).
- The patient receive at least one transfusion after week 16 and before end treatment (No / Yes) (data in section “Supportive Care Record”).

In each of the studied moments, it will be shown the number of transfusions per patient. In addition, for total of transfusions, it will be shown the type of transfusion (Platelets / RBC).

It will be performed:

- Analysis of contingency tables between number of patients with transfusions before start treatment and before week 16, using chi-square or Fisher's exact test.
- Analysis of contingency tables between number of patients with transfusions before start treatment and after week 16, using chi-square or Fisher's exact test.

It will be calculated:

- The period of time where patients did not receive any platelet or RBC transfusions during the treatment period, calculated as the difference between the number of days in treatment and the number of days with transfusions.

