6.3 Concomitant medications

The patient must be told to notify the investigational site about any new medications he/she takes after the start of the study drug. All medications (other than study drug) and significant non-drug therapies (including physical therapy, herbal/natural medications and blood transfusions) administered during the study, and those taken 30 days prior to study entry must be listed on the Concomitant Medications CRF.

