7.2 Periods/visits

7.2.1 Screening/baseline

Prospective patients will be scheduled for a Screening/baseline period by study site staff. The window for this visit is Day -28 to Day 0. Informed consent must be signed before any screening procedure.

Several clinical data recorded at screening visit for every patient will be reviewed by the Coordinating Investigator and the Novartis' Medical Team to verify his/her eligibility for the study at the site before treatment starts.

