## 2.2 Study Design

This study is designed as an open-label, single-arm phase II study, in which patients diagnosed with primary or secondary PGF after allo-HSCT will be treated with eltrombopag up to week 36 or until the patient's premature withdrawal. If patient terminates eltrombopag for any of the reasons established in the withdrawal criteria, he/she will be followed for safety up to 30 days after the last dose of eltrombopag, unless he/she withdraws the consent, dies or is lost-to follow-up.

The primary efficacy endpoint is the overall hematologic response rate (partial and complete) by 16 weeks after the initiation of eltrombopag. Eltrombopag will be initiated on day 1 at a dose of 150 mg once daily (75 mg daily in Asian ancestry patients) and will be continued up to 36 weeks.

The study will consist of the following periods:

- Screening Period (baseline): the patient will be invited to participate in the study, after being informed of its characteristics. The patient screening criteria will then be reviewed, and the procedures established in the evaluation schedule will be performed.
- Treatment Period: from administration of the first dose of eltrombopag until time when patient permanently stops taking study treatment for any reason or until 36 weeks have passed.
  - Only patients with a partial or complete response at week 16 will continue to receive eltrombopag until loss of response (defined as a decrease in blood counts to levels that do not continue to meet the criteria for response established in this protocol), unacceptable toxicity, or discontinuation for any other reason.
  - Patients who discontinue eltrombopag because efficacy, will continue in the study and attend the scheduled visits of Treatment Period as per protocol. If loss of response occurs, eltrombopag will be reintroduced at the last effective dose.
- During the Treatment Period, patients will be evaluated weekly during the first month, every 2 weeks during the next 2 months and subsequently every 4 weeks until week 24. For the last 3 months, patients will be followed every 6 weeks.
- Final Visit (or Early Withdrawal): this visit will take place 30 days after completion of the Treatment Period, or premature patient withdrawal.

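### SAP 10.4 compares any-transfusion indicators over windows of unequal length and drops the protocol's denominator, so the result cannot be read as transfusion independence

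*SAP*

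**What the plan says.** Protocol 10.5.1 defines the endpoint as "the percentage of patients who were previously transfusion-dependent and do no longer require a RBC or platelet transfusion", before and after the first 16 weeks, with a 95% confidence interval. The protocol summary and Table 3-1 use the same restricted population.

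SAP 10.4 (Secondary objective 3) replaces this with three indicators:

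- "The patient receive at least one transfusion before start treatment (No / Yes"
- "The patient receive at least one transfusion after start treatment and before week 16 (No / Yes"
- "The patient receive at least one transfusion after week 16 and before end treatment (No / Yes"

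The first is cross-tabulated with each of the other two by chi-square or Fisher's exact test. SAP section 4 assigns all analyses except adverse events to the Full Analysis Set. SAP 10.4 gives no look-back length, no minimum transfusion-free interval, no lag after Day 1 and no adjustment for time at risk.

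It also reports transfusions per patient in each period, the product type across all transfusions, and transfusion-free time, taken as treatment days minus days with a transfusion.

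**The concern.** The probability of at least one event rises with the length of the window, whatever the drug does. If the baseline window is much shorter than the on-treatment window, the share transfused can rise while the transfusion rate falls.

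The second window also opens on Day 1, before any effect can be expected. One transfusion in the first week marks a patient as transfused for all 16 weeks, even if that patient responds later and needs no more.

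The third window has a different problem. Its content depends on who is still on treatment, and that is decided by response at week 16.

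At stake is whether a reader of the report can learn what share of previously dependent patients became transfusion-free.

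**Working it through.** The documents give no figure for this endpoint, so there is nothing of the plan's own to reproduce.

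**Window lengths**

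- *Day 1 to week 16.* Protocol Table 7-1 places week 16 at Day 113, so the window is 112 days.
- *Week 16 to end of treatment.* Treatment starts on Day 1 "and will be continued up to 36 weeks" (SAP 2.2). That is 252 days, and 252 − 112 = up to 140 days.
- *Before treatment.* The SAP is silent. The only look-back for transfusions is in Protocol 6.3, which covers all medications including transfusions: "those taken 30 days prior to study entry must be listed on the Concomitant Medications CRF". The glossary places entry at consent, and Protocol 7.2.1 says of screening: "The window for this visit is Day -28 to Day 0". If this rule governs, the look-back before Day 1 is 30 to 30 + 28 = 58 days.

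**Day 1 to week 16**

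Formula: P(at least one in T days) = 1 − exp(−rate × T). Assumed rate before treatment: 1 per 28 days. Assumed rate on treatment: half of that.

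On treatment: 1 − exp(−0.5 × 112/28) = 1 − exp(−2) = 86%.

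| Look-back (days) | Share before treatment | Share Day 1 to week 16, rate halved | Rate reduction needed before the share falls (1 − look-back/112) |
|---|---|---|---|
| 30 | 1 − exp(−30/28) = 66% | 86% | 73% |
| 44 | 1 − exp(−44/28) = 79% | 86% | 61% |
| 56 | 1 − exp(−2) = 86% | 86% | 50% |
| 58 | 1 − exp(−58/28) = 87% | 86% | 48% |

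Other assumptions, all with a 30-day look-back:

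- At 2 per 4 weeks, a halved rate moves the share from 88% to 98%.
- With gamma-Poisson variation between patients at a mean of 1 per 30 days, a halved rate moves it from 50.0% to 65.1% (k = 1) or from 42.3% to 54.0% (k = 0.5).

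**Effect of opening the window on Day 1**

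Suppose the rate stays at 1 per 28 days until week 8 and transfusions then stop completely. The share transfused by week 16 is 1 − exp(−56/28) = 86%, the same as for a halved rate. Eight transfusion-free weeks leave no trace in the indicator.

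**Week 16 to end of treatment**

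Only week-16 responders continue (SAP 2.2). The SAP does not say whether the others count as No or are left out. Take the 66% baseline share (30-day look-back) and the protocol's assumed 45% response:

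- Continuing patients only, rate halved: 1 − exp(−0.5 × 140/28) = 92%, an apparent increase.
- Full Analysis Set, the rest counted No, no effect on the rate: 0.45 × (1 − exp(−140/28)) = 0.45 × 0.993 = 45%, an apparent decrease.

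Selection adds to this. Protocol 7.3.1.1 makes transfusion independence part of a platelet or hemoglobin partial response, so patients are partly chosen on the outcome being compared.

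**Equal 28-day windows, same assumptions**

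Before: 1 − exp(−1) = 63%. In the 28 days ending at week 16 with the rate halved: 1 − exp(−0.5) = 39%. The direction is now correct.

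**The case against.** Five points can be made for the plan.

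1. *The look-back is inferred.* The 30 days come from the Concomitant Medications page, whereas SAP 10.4 draws on the Supportive Care Record. This stands. It is why the result is given over a range, and why the increase vanishes at 56 days. Beyond 56 days a halved rate would lower the share.
2. *The table can be read within patients.* The cell for transfused before and not after comes close to the protocol endpoint. This stands in part: the title quantity, a rising share, arises from comparing margins. The cell still requires 112 clear days from Day 1. With a halved rate only exp(−2) = 14% of previously transfused patients would meet it, against exp(−0.5) = 61% for a 28-day window.
3. *Other summaries are planned.* They are, and rates could be derived from counts and treatment duration. As specified, none is per unit time. A patient transfused weekly for 16 weeks scores 112 − 16 = 96 transfusion-free days.
4. *The week-16 split is the protocol's own.* True, and it should be kept as a description.
5. *The planned test would rarely give a false signal of harm.* At 33 patients, 66% against 86% is about 22 against 28 or 29. Fisher's test treating these as independent samples gives p = 0.15 or 0.08. This stands; the damage is to the estimate rather than through a significant p-value.

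A reader might go further and infer that the plan biases the whole endpoint against the drug, or that a halved rate must appear as an increase. The documents support neither. Only one window opens on Day 1, the comparison after week 16 can favour the drug, and the size of any increase depends on an unstated look-back. Nor do they rank this as a main benefit endpoint: it is one of six secondary objectives in a single-arm study.

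**Conclusion.** The point holds. SAP 10.4 tests quantities that are not comparable and does not specify the percentage that the protocol asks for.

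For Day 1 to week 16, a halved transfusion rate shows as anything from a 21-point rise (65.7% to 86.5%, 30-day look-back) to practically no change (58 days). This rests on Poisson transfusions, an assumed rate of 1 per 4 weeks, and the 30 to 58 day look-back inferred from the protocol. At high transfusion rates both shares approach 100% and a benefit is hidden rather than reversed.

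The comparison after week 16 is uninterpretable in either direction.

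The primary endpoint and the sample size are unaffected. The change should be made, but it is not critical to the trial's main conclusion.

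**What to change.** Amend SAP 10.4 before database lock:

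- Keep the before/after week 16 split as a description, without the tests.
- Base the transfusion-independence percentage and its 95% confidence interval on equal windows, for example the 28 days before Day 1 against the 28 days ending at week 16, and likewise at weeks 24 and 36.
- Analyse platelets and red cells separately. The denominator is patients transfused with that product in the baseline window; independence means no transfusion of that product in the later window.
- State how patients withdrawn or off treatment count at each time point, for example as not independent.
- Report transfusions per 4 weeks at risk in each period.

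The cost is mainly SAP wording, since Protocol 7.3.1.2 already has transfusion need monitored at each visit. The window length is a choice and must be fixed in advance; 28 days is an example. It must also be confirmed that the Supportive Care Record holds dated transfusions for the 28 days before Day 1. If the sponsor regards the equal-window definition as changing the protocol endpoint rather than making it operational, that should be documented as such.
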